## 5.6 Treatment compliance

Each patient is expected to comply with the treatment regimen and diary recording during the study. The administration of the study drugs should be recorded appropriately by the research coordinator. Compliance with the study drug will be assessed by comparing the number of tablets

dispensed minus the number of tablets returned versus the number of tables that should have been taken (1 tablet per day). Compliance with the diary will be assessed at each study visit.

### **5.6.1      Accountability**

The study drug provided for this study will be used only as directed in the CSP.

The study personnel will account for all study drugs dispensed to and returned from the patient. This record-keeping consists of a dispensing record that includes the identification of the person to whom the study drug is dispensed, the quantity and the date of dispensing, and the amount of any unused study drug returned to the investigator. This record is in addition to any drug accountability information recorded. Patients must return unused study drug supplies to the investigator at each visit in which new study drug is dispensed, and at the final visit of the treatment period.

Study site personnel will account for all received study drugs. Once monitored, study drug will be destroyed on site in accordance with appropriate regulatory laws.

## **5.7      Discontinuation of investigational product**

Reasons why a subject may discontinue or be withdrawn from the study include but are not limited to AE, subject request, protocol violation, subject noncompliance, and study termination. When a subject discontinues or is withdrawn, the investigator will notify the sponsor, and when possible assessments will be performed, and all study drugs and the diary should be returned by the patient.

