### **3.2.5 Early Withdrawal**

If the patient begins the randomized phase of the study but withdraws prior to the end of 14 days of treatment, every effort will be made to complete Visit 3. If a visit is not possible, a telephone contact will be attempted, during which information will be elicited about study drug use, change in medical status, other drugs taken and AEs. Pick-up or mailing of the unused study medications and diaries will be arranged.

If the patient begins the open-label extension phase but withdraws prior to the end of 14 days of treatment, every effort will be made to complete Visit 4. If a visit is not possible, a telephone contact will be attempted, during which information will be elicited about study drug use, change in medical status, other drugs taken and AEs. Pick-up or mailing of the unused study medications and diaries will be arranged.

If the patient completes the randomized phase of the study and chooses not to proceed into the open-label extension, the data collected during Visit 3 (completion of RCT) will be used as the end-of-study visit and is not considered an early withdrawal.

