### **5.7.1    Procedures for discontinuation of a subject from investigational product**

Participation in the study is voluntary and a patient can withdraw from the study at any time. Besides voluntary withdrawal, a patient can be removed from the study by the investigator for the following reasons.

- Serious adverse event related to the investigational product
- Non-compliance with the study protocol/fails to follow instructions of study personnel
- Closure of the study

If a subject prematurely discontinues from the study, for a reason other than death, after receiving at least one dose of study drug they will be asked to return to the study site to complete all assessments for visit 4 end of treatment visit. This end of treatment visit should be scheduled as soon as possible after the patient discontinues from the study and there will also be a follow-up telephone call approximately 7 days after the patient's last dose of study drug. Any patient who discontinues due to an adverse event will be followed until the event has resolved or is felt to be stable as determined by the investigator.

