### **6.2 Efficacy**

#### **6.2.1 PAC-SYM**

The PAC-SYM questionnaire [10] is a 12-item questionnaire that evaluates the severity of symptoms of constipation in 3 domains (stool, rectal, and abdominal symptoms) on a 5-point Likert scale ranging from 0 (absent) to 4 (very severe) in the 2 weeks (14 days) prior to assessment. The items of the instrument were developed through literature review and patient interviews. The PAC-SYM has been extensively validated for constipation and is available in several languages that facilitate its use in multinational studies. The questions will take approximately 5 minutes to answer. The PAC-SYM will be administered to patients at Visits 2,3 and 4.

The PAC-SYM questionnaire will be completed by patients on paper forms provided by the study site. Study staff will provide initial instruction on how to fill out the questionnaire. Patients are to fill out the questionnaire in a quiet area, without any help from family, friends, or study staff. Patients are to fill out the PAC-SYM questionnaire prior to any interventions or discussions regarding their OIC with the study staff or the investigator.

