## **9. DATA MANAGEMENT**

### **9.1 Electronic case report form**

The eCRF and the protocol are both confidential. The eCRF will be programmed into the eDC system. All study sites will need internet access to access the eCRFs and will only have access to data for patients at their own study sites. [REDACTED] will have access to data at all study sites.

All eCRFs are to be completed by an authorized member of the study staff and reviewed and signed by the investigator. All entries, corrections, and alterations are to be made by the responsible investigator or an authorized member of the investigational staff. All eCRFs are to be completed in a manner that ensures accurate interpretation of data.

It is each investigator's responsibility to ensure that all discontinued orders or changes in the study or other medications entered on the patient's eCRF correspond to the entries on the patient's medical records. The eCRFs for any patient leaving the study should be completed at the time medication is terminated for whatever reason.

The eCRFs must accurately reflect data contained in patient's records (eg, source documents).

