##### **10.2.1.1 SBMs Responder Rate**

A SBM is defined as a BM without rescue laxatives in the previous 24 hours. Days with no BMs should be recorded as zero, rather than missing. This diary data will be used to identify SBMs. The weekly SBM frequency within each time period will be calculated for each patient as:

(Total number of SBMs during the time period of interest/number of days) x 7,

where the denominator is the number of days during the time period in which the patient records data. If less than 4 days of data are recorded within a particular week, the data for that week will be considered insufficient and the rate will be set to missing for that week.

A responder is a patient with  $\geq 3$  SBM in a week and at least one SBM/week increase over baseline for the two weeks during which the study drug is taken. For the purposes of the analysis, the proportion of responders will be evaluated during the randomized period, and also during the extension period. The randomized period permits a comparison of response rates for those who received naloxegol and those who received placebo. The responder rate during the extension period for those patients who entered the extension period after having had placebo will be evaluated as supportive of the response rate determined during the randomized period.

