### **11.2 Outcome analyses**

The analysis of the randomized dataset will evaluate an intent-to-treat (ITT) population, defined as all randomized patients participating. These analyses will be complemented by descriptive data from the open-label extension period.

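### Stopping study drug in the blinded phase ends diary and questionnaire collection, so the ITT efficacy comparison has no data after stopping

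*Combined protocol and SAP*

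**What the plan says.** **On stopping.** Section 5.7 says that when a subject discontinues or is withdrawn, "when possible assessments will be performed, and all study drugs and the diary should be returned by the patient". Section 5.7.1 asks for the Visit 4 assessments: "This end of treatment visit should be scheduled as soon as possible after the patient discontinues from the study". It also lets the investigator remove a patient from the study for non-compliance. Section 6.3.9 likewise takes patients with drug-related liver enzyme elevation out of the study, not only off the tablet. Section 9.1 adds: "The eCRFs for any patient leaving the study should be completed at the time medication is terminated for whatever reason".

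Section 3.2.5 covers the randomized phase separately. If a patient "withdraws prior to the end of 14 days of treatment, every effort will be made to complete Visit 3"; failing that, a telephone contact is tried, and pick-up or mailing of the diary is arranged. It gives no timing for that visit.

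**On adverse events.** Collection runs from consent to the follow-up contact (6.3.3). Section 5.7.1 provides a "follow-up telephone call approximately 7 days after the patient's last dose of study drug". Unresolved events are followed, and events after the last dose are summarized (10.1.1).

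**On analysis.** Section 11.2 "will evaluate an intent-to-treat (ITT) population, defined as all randomized patients participating", and section 11.2.2 divides responders by all ITT patients in the arm. Weekly SBM frequency (10.2.1.1) is scaled to 7 days, "where the denominator is the number of days during the time period in which the patient records data"; a week with fewer than 4 recorded days is set to missing. PAC-SYM rates symptoms "in the 2 weeks (14 days) prior to assessment", and PAC-QOL has the same recall (6.2.2).

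**The concern.** An ITT comparison over a 14-day period needs outcomes over those 14 days for everyone randomized, on or off the tablet. Here the patient who stops early hands back the instrument that records bowel movements, straining, stool form, pain and rescue use, and the questionnaires are brought forward to the closing visit.

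That patient's efficacy result is then settled by rules written for other purposes: a pro-rating rule, a minimum-days rule, a recall period longer than the time on treatment, and a denominator. None of these is stated as a rule for early stoppers. The pilot is meant to supply an effect size for a definitive trial (section 11.1), so with 22 per arm and no replacement a few such patients matter.

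**Working it through.** **Inputs.** Randomized period 14 days (5.4.2). PAC recall 14 days (6.2.1, 6.2.2). Weekly rate = SBMs ÷ recorded days × 7, with at least 4 recorded days (10.2.1.1). A responder has at least 3 SBMs in a week and a gain of at least 1 per week over baseline, for the two weeks on drug (10.2.1.1). 22 per arm (11.1).

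**Assumptions.** First dose on Day 1, diary kept up to the last dose, closing visit on the day after it.

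**1. PAC-SYM and PAC-QOL.** With a last dose on Day d, the recall holds d treated days and 14 − d untreated days.

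| Last dose | Pre-treatment days in recall | Share |
|---|---|---|
| Day 3 | 11 of 14 | 79% |
| Day 5 | 9 of 14 | 64% |
| Day 7 | 7 of 14 | 50% |
| Day 10 | 4 of 14 | 29% |
| Day 13 | 1 of 14 | 7% |

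The pre-treatment days also fall within the recall of the Visit 2 baseline form, so the change score partly compares the same days with themselves. If symptoms dropped fully at the first dose and recall averaged evenly, the share of the change seen would be d/14: 5/14 = 36% for Day 5 and 7/14 = 50% for Day 7. Pre-treatment time is the larger part only for a last dose before Day 7.

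**2. Weekly SBM rate.**

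| Last diary day | Week 1 | Week 2 |
|---|---|---|
| 1 to 3 | missing | missing |
| 4 to 6 | scored on 4 to 6 days | missing |
| 7 to 10 | scored on 7 days | missing |
| 11 to 13 | scored on 7 days | scored on 4 to 6 days |

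With 4 days in week 2, 2 SBMs give 2/4 × 7 = 3.5 per week and meet the 3-per-week component. With 5 days, 2 SBMs give 2.8, so 3 are needed; with 6 days, 2 give 2.3, so again 3 are needed. Only a last diary day of 11 lowers the count required. That patient must still meet the week 1 criterion and the gain over baseline.

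Pro-rating does not inflate consistently. If SBMs followed a Poisson process at a constant 2 per week, the chance of reaching the threshold would be 0.32 on 4 days, 0.17 on 5, 0.25 on 6 and 0.32 on all 7. At 3 per week the figures are 0.51, 0.36, 0.47 and 0.58. The problem is that the off-drug days are absent, not that the partial week is always flattering.

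For a last diary day before Day 11, week 2 is missing. If response requires both weeks, the patient cannot be shown to respond but stays in the ITT denominator, and so counts as a non-responder without any rule saying so.

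**3. Size per patient.** 1/22 = 4.5 percentage points in that arm's response rate.

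**4. Pain and opioid dose.** The interval means use only days with data (10.1.2, 10.1.3), so they end at the last diary day. Section 11.2.1 summarizes them by arm and tests change within each arm.

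**5. Which closing visit.** Section 3.2.5 names Visit 3 for a randomized-phase withdrawal; section 5.7.1 names Visit 4. Visit 3 includes blood samples and ECG (3.2.3); Visit 4 does not (3.2.4). Sections 10.1.4 and 10.1.5 calculate laboratory and ECG change to Visit 3.

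**The case against.** The operative sentences in 5.7 and 5.7.1 speak of leaving the study, so the equation of stopping tablets with leaving rests partly on their headings and on 9.1. Removal for non-compliance is optional. This is fair, but no section says what happens to a patient who stops tablets and is willing to stay, so the gap remains.

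A reader might infer that all outcome collection ends at stopping. It does not. Adverse events, the primary endpoint, continue to about 7 days after the last dose, and the closing visit still yields PAC-SYM, PAC-QOL and NRS. The treatment-emergent definition in 10.1.1 stops at the last dose, but later events are collected and summarized. A reader might also infer that the eCRF is closed: section 9.1 says completed, and locking follows the investigator's signature (9.2). The prompt closing visit rests on 5.7.1 alone.

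Pain leading up to stopping is not lost, since the NRS is recorded every evening; only later diary pain is. With within-arm tests only, no planned between-arm pain test is distorted.

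Finally, in a small pilot of very ill patients, whether to follow people off drug is partly a choice of what to estimate. That stands, but the plan has chosen ITT and its data collection should match.

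**Conclusion.** The point holds for efficacy data from the diary and questionnaires. After stopping in the blinded phase nothing further is planned for these outcomes, and no rule says how early stoppers are scored. The pain and opioid summaries are cut at the same place.

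The consequence varies by endpoint. PAC change scores are diluted with pre-treatment time, heavily for stops in the first week and slightly near Day 13, assuming a next-day visit. For the responder rate, most early stoppers become non-responders by default if both weeks are required, and a narrow group (last diary day 11 to 13) is scored on a partial week. It would therefore go too far to say that the ITT comparison becomes an on-treatment one.

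The number affected cannot be given. One might read the 80% retention goal as allowing 8 of 44 patients (18%) to be lost this way, but section 10.2.2 sets that goal for completing the whole study and calculates retention by site. Stopping may differ between arms, but the documents give no discontinuation rates, so that remains an assumption. This is a cheap improvement worth making, not a defect in the primary safety aim.

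**What to change.** In 3.2.5, 5.7, 5.7.1 and 9.1, separate stopping study drug from withdrawing from the study. Ask a patient who stops drug in the blinded phase and has not withdrawn consent to:

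- keep the diary through Day 14;
- complete PAC-SYM, PAC-QOL and NRS at the scheduled Visit 3 time, by telephone if needed.

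Record the date and reason for stopping. State in 11.2 that these data enter the ITT comparison, and how a patient with a missing week is counted. Say also how bowel movements are handled if another constipation treatment starts after stopping, since the SBM definition excludes only those following rescue laxatives.

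Leave the existing early-stopping safety visit and adverse-event follow-up in place. Reconcile 3.2.5 (Visit 3) with 5.7.1 (Visit 4), because their assessments differ.

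**Cost.** Amendment wording, up to two more weeks of a diary the patient already has, and one questionnaire contact. The sample size does not change. The burden falls on ill patients; some will decline, and their data will stay missing.

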### **5.7.1    Procedures for discontinuation of a subject from investigational product**

Participation in the study is voluntary and a patient can withdraw from the study at any time. Besides voluntary withdrawal, a patient can be removed from the study by the investigator for the following reasons.

- Serious adverse event related to the investigational product
- Non-compliance with the study protocol/fails to follow instructions of study personnel
- Closure of the study

If a subject prematurely discontinues from the study, for a reason other than death, after receiving at least one dose of study drug they will be asked to return to the study site to complete all assessments for visit 4 end of treatment visit. This end of treatment visit should be scheduled as soon as possible after the patient discontinues from the study and there will also be a follow-up telephone call approximately 7 days after the patient's last dose of study drug. Any patient who discontinues due to an adverse event will be followed until the event has resolved or is felt to be stable as determined by the investigator.

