### **3.2.3 Visit 3 – Open Label Treatment Period (Part 2)**

After 14 days of study drug, the patient will have Visit 3, which must occur within 3 days of the end of the randomized period. At this Visit, the following procedures will be performed:

- Collect and review paper diary and dispense new diary
- Collect empty and unused rescue medication and additional rescue medication may be dispensed as needed.
- Brief physical exam as determined necessary by the investigator
- Collect empty containers and unused study drug and review for compliance
- Dispense open-label medication and instruct patient and caregiver on daily use
- Review and record other scheduled medications and doses, and ‘as needed’ medications and doses
- Collect and record adverse events that have occurred since last visit
- Measure sitting blood pressure, pulse and respiratory rate
- Collect blood samples for local laboratory evaluations
- Obtain 12 lead ECG
- Have patient complete the following validated questionnaires: PAC-SYM, PAC-QOL, and NRS for pain

After Visit 3, patients will take one dose of study medication (naloxegol 25 mg) daily for 14 days and may use rescue laxative as instructed. He or she will again complete the daily diary to capture information about study outcomes. The research coordinator may telephone the patient as needed to answer questions and encourage adherence to study procedures. The research coordinator must contact the patient at 72 hours (+/- 24 hours) after Visit 3.

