### **3.2.4 Visit 4 – End of Treatment or Withdrawal**

After 14 days of open-label study drug, the patient will have Visit 4, which must occur within 3 days of the end of the treatment. At this Visit, the following procedures will be performed:

- Collect and review daily paper diary
- Collect empty and unused rescue medication
- Collect empty containers and unused study drug and review for compliance
- Review and record other scheduled medications and doses, and ‘as needed’ medications and doses.
- Collect and record adverse events that have occurred since last visit
- Measure sitting blood pressure, pulse rate, and respiratory rate
- Have patient complete the following validated questionnaires: PAC-SYM, PAC-QOL, and NRS for pain

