### **6.3.11 ECG**

Digital ECGs for all patients at all centers will be conducted by the study site. ECGs will be performed at Visit 1 and 3, after the patient has been resting in a supine position for at least 10 minutes. All ECGs will be documented by recording date, time, heart rate, QRS duration, PR interval, RR interval, QT and QTcF.

The investigator will judge the overall interpretation as normal or abnormal. If abnormal, it will be decided as to whether or not the abnormality is clinically significant or not clinically significant and the reason for the abnormality will be recorded on the eCRF, if the investigator considers it clinically significant. Abnormal values shall not be recorded as AEs unless deemed clinically significant.

It is the investigator's judgment whether the findings/results on the ECG assessment are clinically relevant or not and whether the findings will result in the discontinuation of the patient from the study based on the inclusion/exclusion criteria or discontinuation criteria.

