#### **10.1.4 Laboratory safety assessments**

Changes from baseline to visit 3 for all patients will be calculated as the post-baseline test value minus the baseline test value. Laboratory test results will also be compared with the laboratory reference ranges, and values that are outside the applicable reference range will be flagged at high or low.

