#### **10.1.5 ECG**

Changes from baseline to visit 3 for ECG interval data and rate data will be derived by subtracting the baseline value from the final assessment data. Marked abnormal values or changes from baseline will be identified based on pre-determine criteria.

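### Sections 3.2.5 and 5.7.1 send a dosed patient who withdraws in the blinded phase to different visits, and only one of those visits includes labs and an ECG

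*Combined protocol and SAP*

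**What the plan says.** Section 3.2.5 divides early withdrawal by phase. For a patient who has begun the randomized phase but "withdraws prior to the end of 14 days of treatment, every effort will be made to complete Visit 3"; a telephone contact is the fallback. Visit 4 is the target only for a patient who withdraws during the open-label extension.

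Section 5.7.1 makes no such division. For any premature discontinuation after at least one dose, other than by death, it says "they will be asked to return to the study site to complete all assessments for visit 4 end of treatment visit".

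The two visits differ in safety content. The Visit 3 list in Section 3.2.3 includes "Collect blood samples for local laboratory evaluations" and "Obtain 12 lead ECG". The Visit 4 list in Section 3.2.4 includes neither. Table 1 marks blood samples and ECG at Visits 1 and 3 only, and Section 6.3.11 agrees for the ECG: "ECGs will be performed at Visit 1 and 3".

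The analysis depends on Visit 3. Section 10.1.4 defines laboratory change as "Changes from baseline to visit 3 for all patients", and Section 10.1.5 refers to "Changes from baseline to visit 3 for ECG interval data and rate data". Section 11.2.1 then summarizes these changes descriptively by treatment group.

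**The concern.** A dosed patient who leaves during the blinded phase falls under both sections, which name different visits. Visit 3 is the only scheduled laboratory and ECG assessment after dosing starts. If the site uses Visit 4, that patient has no scheduled post-dose value for either and drops out of the change summaries, although the laboratory definition is meant to cover everyone.

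Those lost need not be a random subset. Section 5.7 lists adverse events among the reasons for stopping, and Section 5.7.1 provides for removal after a drug-related serious adverse event. Patients who stop because they tolerate the drug poorly are the ones whose post-dose laboratory and ECG values matter most for a safety aim. The rule in Section 6.3.9 for raised transaminases also needs a post-dose sample before it can be applied.

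**Working it through.** The plan gives no figure to reproduce here. The check compares the texts and then works out a rough scale.

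**Step 1: do both rules apply to the same patient?** Yes. Section 5.7.1 opens with voluntary withdrawal, adds removal by the investigator, and then sets one procedure for every premature discontinuation after a first dose other than by death. It therefore cannot be read as covering removals only, with 3.2.5 covering withdrawals.

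**Step 2: what does each visit collect?**

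| Assessment | Visit 3 (3.2.3) | Visit 4 (3.2.4) |
|---|---|---|
| Diary, rescue laxative and study drug return | Yes | Yes |
| Medications, adverse events, vital signs | Yes | Yes |
| PAC-SYM, PAC-QOL, NRS | Yes | Yes |
| Blood samples | Yes | No |
| 12-lead ECG | Yes | No |
| Brief physical exam | As needed | No |

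Visit 3 contains every Visit 4 assessment. A site that completes Visit 3 meets both sections. A site that completes only Visit 4 meets 5.7.1 but not 3.2.5.

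**Step 3: does other text settle it?**
- The heading of 3.2.4 mentions withdrawal, which favours 5.7.1, but its text ties the visit to the end of open-label drug: "After 14 days of open-label study drug, the patient will have Visit 4".
- The last paragraph of 3.2.5 lets Visit 3 serve as the end-of-study visit, but only for patients who complete the randomized phase and decline the extension.
- Section 5.7 asks for assessments where possible and names no visit.
- Sections 6.3.8 and 6.3.13.2 allow unscheduled tests but do not require them.

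Nothing ranks 3.2.5 against 5.7.1.

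**Step 4: scale.** No blinded-phase dropout rate is given. The inputs are 44 randomized patients, 22 per arm (Section 11.1), and a retention goal of 80% (Section 10.2.2). The goal is a target for the whole study, not a forecast, and using 44 as its denominator is an assumption.

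- Non-completers if the goal is just met: (1 − 0.80) × 44 = 8.8, or (1 − 0.80) × 22 = 4.4 per arm.
- Patients under the conflicting rules = 8.8 × share who stop in the blinded phase:

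| Assumed share | Patients of 44 | Per arm of 22 | Percent of arm |
|---|---|---|---|
| 0% | 0 | 0 | 0% |
| 50% | 4.4 | 2.2 | 10% |
| 100% | 8.8 | 4.4 | 20% |

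Within each scenario, these counts are the most that could lose laboratory and ECG data. A site that completes Visit 3 loses none, and deaths and telephone-only contacts yield no tests under either section.

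**The case against.** The strongest reply is that the two sections can both be obeyed. Completing Visit 3 satisfies each of them, 3.2.5 is the more specific rule, and a site that does only Visit 4 has overlooked an explicit instruction. That is a sound guide to what a careful site should do, but the protocol does not state it. Section 5.7.1 is the one titled for discontinuation procedures, and the 3.2.4 heading points the same way, so the Visit 4 reading is a natural one.

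It is also fair to say that the stakes are limited. The primary safety endpoint in Section 10.1 is the between-group difference in adverse events, which both visits collect. The laboratory and ECG summaries are descriptive, with no test or decision rule. Patients who stop for an adverse event are followed until it resolves or stabilizes, and investigators are told to keep a low threshold for extra tests. Section 3.2.1 accepts a screening ECG up to 12 months old, so some ECG changes would be measured from a weak baseline. All of this stands and limits the severity, but none of it requires a post-dose laboratory sample or ECG from every patient who stops.

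The scale is uncertain too. Dropout could exceed what the retention goal implies, so 8.8 is not an absolute upper bound. If patients who decline the extension count as non-completers, the 8.8 includes people who already have Visit 3 tests. How many sites would follow 5.7.1 alone is not known.

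**Conclusion.** The contradiction is real and should be corrected. For a dosed blinded-phase withdrawal other than by death, the protocol names two different visits, and following 5.7.1 as written forgoes the only scheduled post-dose laboratory and ECG values. The adverse event endpoint, vital signs and questionnaires are unaffected. So are patients who stop in the open-label phase, since they already have Visit 3 tests.

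The textual finding is firm; the amount of data at risk is not. The range of 0 to about 9 patients of 44 assumes that the retention goal is just met, that its denominator is all randomized patients, and that anywhere from none to all of the non-completers stop in the blinded phase. The actual loss could be zero if every site follows 3.2.5. With 22 per arm, even the middle scenario of 2.2 patients is a tenth of an arm, and it would fall on patients who may be stopping for tolerability.

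**What to change.** Amend Section 5.7.1 so that it matches 3.2.5. Suggested wording: a patient who discontinues during the randomized phase completes the Visit 3 assessments, including laboratory samples and 12-lead ECG, without dispensing of open-label drug; a patient who discontinues during the open-label phase completes the Visit 4 assessments; if a visit is not possible, the telephone contact in Section 3.2.5 applies. Patients who complete open-label treatment attend Visit 4 as now.

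Aligning the 3.2.4 heading and adding a footnote to Table 1 would help but are optional. The cost is one sentence of protocol wording. No test is added beyond those 3.2.5 already requests.
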